#### 9.2.2. Part 2 challenge study sample size

Approximately 50 participants will be enrolled in Part 2 of the study for an estimated total of 25 evaluable participants per intervention group.

The sample size of 50 challenged and evaluable participants (25 Palivizumab treated participants and 25 placebo participants) in Part 2 of the study was calculated based on the assumptions of an infection rate of 73.7%, (infection rate obtained from placebo group participants from 7 studies totalling 216 RSV challenged participants, with 160 infected), a mean area under the viral load-time curve (VL-AUC) of RSV-A Memphis 37b as determined by qRT-PCR on nasal samples in the placebo arm of 20.3 hours\*Log10 copies/mL with corresponding SD of 17.8 and CV of 87.9%. Based on these assumptions, and using a 0.05 two-sided type one error probability, the 50 challenged and evaluable participants will ensure a power of 80% to the detection of a reduction of at least 70% in VL-AUC.

Using a 0.1 two-sided type one error probability, the 50 challenged participants will ensure a power of 80% to the detection of a reduction between 60 and 65% in VL-AUC.

Reduction in VL-AUC	50%	55%	60%	65%	70%	75%	80%
N/group for 80% power, 5% two-sided	49	40	34	29	25	22	19

hVIVO template identifier: (G\_0687) v3.0

Power, 5% two-sided with 25 participants	0.522	0.601	0.660	0.729	0.800	0.843	0.886
Power, 10 % two sided with 25 participants	0.644	0.716	0.781	0.835	0.881	0.916	0.940

# 9.3. Populations for Analyses

The following populations are defined:

# Part 1

Population	Description		
Enrolled	All participants who signed the informed consent.		
Evaluable	All participants assigned to study intervention and who take a dose of study treatment and who complete visit Day 12 Except those participants with protocol deviations that lead to exclusion.		
Safety Analysis Set	All participants assigned to study intervention and who take a dose of study treatment.		
PK Analysis	The PK Analysis set is defined as all participants with at least one post-dose PK result.		

#### Part 2

Population	Description			
Enrolled	All participants who signed the informed consent and randomised to study treatment.			
Evaluable	All participants randomly assigned to study intervention and who take a dose of study treatment, are given viral challenge, and who complete quarantine. Except those participants with protocol deviations that lead to exclusion.			
Safety Analysis	All participants randomly assigned to study intervention and who take a dose of study intervention, regardless of whether they received the challenge virus or not. Participants will be analysed according to the intervention they actually received.			
PK Analysis	The PK Analysis set is defined as all participants with at least one post-dose PK result.			

The primary analysis will be on the evaluable population. The safety evaluation will be performed on the Safety Analysis population.

# 9.3.1. Subgroup Analysis

A 'Laboratory confirmed infected' subgroup will be identified and certain pre-specified analyses (to be documented in the SAP) will also be performed.

## 9.4. Interim Analysis

The Statistical Analysis Plan will describe the planned interim analyses in greater detail.

Interim analyses in Part 2 will only assess the Placebo group infectivity, that impacts powering assumptions.

# 9.5. Sequence of Analysis

A specific statistician (name 'unblinded statistician' in the remainder of this document) will be dedicated to performing all unblinded analyses conducted before the final database lock and unblinding. As soon as the first unblinded analysis, the unblinded statistician will remain independent from the project to maintain the study team blinded.

#### Part 1

• The analysis of the PK data obtained from Part 1 of the study, confirming the dose to be used in Part 2 will be conducted as soon as part 1 will be completed. The PK assessment to progress from Part 1 into Part 2 is as described in Section 9.6.10

#### Part 2

• An interim analysis aiming at reassessing the sample size will be performed once at least 50% of the planned number of challenged participants have been challenged and released from the quarantine unit. This analysis will be performed by the unblinded statistician. This analysis will be solely to confirm the powering assumptions (i.e. infection rate) within the Placebo group and may allow for additional participants to be included into the study, if needed to ensure the study is not underpowered. A second interim look to the placebo infection rate may be conducted when the targeted enrolment is reached, to further consider increasing the sample-size.

As the interim look(s) will not compare the two treatment groups on the efficacy endpoints, and as the study is exploratory and statistical testing is not its primary goal, no adjustment to the type I error rate will be made.

- The main analysis will be performed when efficacy (qRT-PCR and categorical symptom scores) clean data up to discharge from quarantine (Day 12) are available from all participants. In addition, PK data that may become available at that time might be analysed as well. The unblinded statistician will be unblinded for these analyses (i.e., will have access to the individual participant treatment assignment). The remaining study personnel will remain blinded (i.e., will not have access to the individual participant treatment assignment) until study end and database lock. No individual listings are expected to be required until End of Study (EOS) and the Investigator will not have access to the treatment allocation up to study end and database lock. This analysis will be considered as final for key efficacy endpoints.
- A final EoS analysis will be performed when all endpoint data (safety and efficacy) up to study end (Day 28) are available and locked. All available tertiary endpoints available at that time may also be analysed in this step. An integrated CSR containing all data will be written and made available to the sponsor and the Investigator. Individual listings will only be provided at this stage.

hVIVO template identifier: (G 0687) v3.0

The final CSR will contain at least the final analyses of endpoints. If the data for tertiary endpoints become available at a later stage, (an) additional analysis/analyses will be performed. These analyses will be documented separately to the CSR and will be made available to the Sponsor and Investigators at that time.

## 9.6. Statistical Analysis

This section is a summary of the planned statistical analyses of the most important endpoints including key endpoints.

## 9.6.1. Statistical Analysis Plan

Data will be analysed and reported using SAS® version 9.4 or later.

The detailed SAP will be developed by Venn Life Sciences and approved by the Sponsor prior to any look at unblinded data. The SAP will give a more detailed description of the report presentations to be produced for Parts 1 and 2 of the study, respectively, expanding on the protocol specified analysis. Any deviation(s) from the original statistical plan should be described and justified in an amendment to the protocol and/or SAP as appropriate and referenced also in the final clinical study report (CSR).

Further post-hoc evaluations of any exploratory endpoints may be conducted and reported separately.

#### 9.6.2. General statistical methods

#### 9.6.2.1. Descriptive statistics

Continuous variables will be summarised using the following statistics: number of available data, number of missing values, mean (and/or geometric mean where applicable), standard deviation, median, Q1, Q3, minimum and maximum values. When relevant, confidence intervals will be computed for the mean or the median.

Categorical variables will be summarised using number of available data, number of missing values, frequency counts for each category and corresponding percentage. Percentages will be calculated using the number of available data as the denominator (i.e. not including missing values). When relevant, confidence intervals will be computed.

#### 9.6.2.2. Inferential statistics and significance testing

Between group comparisons will be performed using appropriate two-sided hypothesis tests at the 5% two-sided significance level.

For normally distributed continuous variables (either raw variable or log-transformed variables) the difference in means, the standard error and the 95% two-sided confidence interval (CI) will be presented. In case of log-transformed variables, in addition to the previous statistics on the log-transformed data, the geometric means and geometric mean ratio and its 95% two-sided CI for the original variable will be presented. The t-test, analysis of covariance, or linear mixed-models for repeated measures will be used, depending on the endpoint. For endpoints that are not normally distributed (such as total symptom scores), the Wilcoxon Rank-Sum test will be used. Details on the method used for each endpoint will be provided in

the SAP. Methods for checking statistical model assumptions and alternative methods of analysis if the assumptions are not fulfilled will be described in the SAP.

For categorical variables, differences in absolute frequency and/or relative risks will be presented, with their 95% two-sided CIs will be presented. Except otherwise specified in the SAP, the Chi-square test will be used to compare frequencies between groups.

As the study is explorative by nature, there will be no attempt to adjust for the multiplicity of endpoints.

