The RSV human challenge model was developed to not only aid understanding of RSV disease, but to also assess the efficacy of RSV antivirals, immunomodulators and vaccines. The RSV-A Memphis 37b challenge strain has been used for over 10 years by both hVIVO and others and has helped assess the efficacy of numerous RSV therapies and vaccines (Lambkin-Williams et al. 2018). Specifically, hVIVO have safely and successfully used the RSV challenge strain in over 1220 healthy participants (18 to 55 years of age) and have also safely completed inoculation of twenty-four participants between 60 and 75 years of age. Additionally, another strain of live RSV (Memphis 37c) has been used as an inoculation agent and was shown to be safe in over 77 healthy young adults across three studies. RSV infection was not associated with any serious adverse side effects. Healthy RSV challenge study participants have approximately 65% to 85% chance of becoming infected with RSV following the administration of the virus (DeVincenzo et al. 2010). Typical RSV illness is characterised by an abrupt onset of rhinitis, nasal stuffiness, fever, malaise, myalgia (muscle aches), and sore throat. In healthy adults, the illness usually resolves without any treatment, with relief of symptoms occurring naturally within 7 to 10 days.

Palivizumab (Synagis™), a humanised monoclonal antibody directed against RSV, has been shown to be effective in reducing hospitalisation due to RSV by approximately 50% in high-risk infants who receive monthly immunoprophylaxis. While several clinical studies with Palivizumab were performed in adults, it is not currently licensed for use in adults. A full summary of the preclinical and clinical experience with Palivizumab (Synagis™). can be found in the Summary of Product Characteristics (SmPC) and "PALIVIZUMAB Summary of relevant clinical and non-clinical data to support the use of Investigational Medicinal Product (IMP) in the clinical trial" document supplementing the SmPC.

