No data exists for Palivizumab in the RSV human challenge model. Further to scientific advice received from the European Medicines Agency (EMA), this exploratory study is intended to establish the margins of effect and variance of prophylactically administered Palivizumab within the RSV-A Memphis 37b challenge model in healthy adult volunteers. This will enable subsequent evaluation of biosimilars (such as MB05) for prophylactic equivalence or non-inferiority to the reference article (Palivizumab), in the RSV human challenge model.

Furthermore, this study will explore the minimal clinically important differences (MCID) between the reference article Palivizumab and Placebo treated groups after inoculation with RSV. The MCID is defined as the smallest difference in score in the outcome of interest that informed what patients or proxies perceive as important, and which would lead the patient or clinician to consider a change in the management (Schunemann and Guyatt 2005). The data obtained from this study will aid in developing MCIDs for each endpoint measure, as appropriate.

The rationale for the study design is presented in Section 4.2.

Please refer to the SmPC for a full summary of the preclinical and clinical experience with Palivizumab (Synagis™).

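### No planned analysis puts a confidence interval on the percentage reduction in VL-AUC that Part 2 is sized on

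*Protocol*

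**What the plan says.** Protocol 2.2 gives the purpose of the study as "to establish the margins of effect and variance of prophylactically administered Palivizumab" in the challenge model, so that biosimilars can later be compared with it. SAP 5.4.1 makes VL-AUC by qRT-PCR the primary efficacy analysis under that objective.

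Protocol 9.2.2, repeated in SAP 2.3.2.2, states the target as a percentage: "the 50 challenged and evaluable participants will ensure a power of 80% to the detection of a reduction of at least 70% in VL-AUC". Every column of the power table is a percentage reduction.

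The analysis rules lead to three kinds of result:

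- **Untransformed t-test.** For normally distributed variables, "the difference in means, the standard error and the 95% two-sided confidence interval (CI) will be presented" (Protocol 9.6.2.2; SAP 5.1.2 has the same sentence).
- **Log-transformed data.** The next sentence adds a geometric mean ratio with a 95% interval. For VL-AUC, SAP 5.4.1 says only that a transformation may be used if the distribution is not normal. It does not name the transformation or say how zeros are treated.
- **Wilcoxon rank-sum test.** This is for endpoints that are not normal. No effect estimate goes with it.

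SAP 5.2.3.2 scores an undetected qRT-PCR result as 0, so a participant who is negative throughout has an AUC of 0. For categorical endpoints, the same general rules already allow relative risks with intervals.

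**The concern.** The trial exists to estimate an effect, so the scale of that effect and its interval are the main product. The plan fixes the scale for sizing (relative, on arithmetic means) but leaves the reported scale to a normality check made after the data are in. The possible results are an absolute difference, a ratio of geometric means or a p-value alone. They are not interchangeable, and none is the quantity used for sizing.

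The absolute difference has a further weakness as an input to a later trial. Its size depends on how many placebo participants become infected, and Protocol 2.1 puts this at "approximately 65% to 85% chance of becoming infected with RSV".

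**Working it through.** **Inputs.** From Protocol 9.2.2: placebo mean 20.3 hours*log10 copies/mL, SD 17.8, infection rate 73.7%, 25 per group, 5% two-sided, 80% power. From Protocol 2.1: infection range 65% to 85%. Two assumptions are not in the documents: uninfected participants have an AUC of 0, and the palivizumab-arm SD takes the values shown below.

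**1. The plan's own figure.** The target is 0.70 × 20.3 = 14.21. With a common SD, n = 2 × [(1.960 + 0.842) × 17.8 / 14.21]² = 24.6, so 25 per group. The same formula returns all seven tabulated sizes (49, 40, 34, 29, 25, 22, 19). Sizing is therefore on arithmetic means over all challenged participants. Reading 20.3 as a mean in infected participants only would need 45 per group.

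**2. What the t-test route reports at the design values.** SE = 17.8 × √(2/25) = 5.03. The interval is 14.21 ± 2.011 × 5.03 = 4.1 to 24.3, with no percentage attached.

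**3. Dependence on infection rate.** The mean in infected participants is 20.3/0.737 = 27.54. Their SD is √[(17.8² − 0.737 × 0.263 × 27.54²)/0.737] = 15.2. For infection rate p, a constant 70% reduction is a difference of 0.7 × p × 27.54, and a fixed difference of 14.21 is a reduction of 14.21/(p × 27.54):

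| Placebo infected | Difference for a 70% reduction | Reduction for a difference of 14.21 |
|---|---|---|
| 65% | 12.5 | 79% |
| 73.7% | 14.2 | 70% |
| 85% | 16.4 | 61% |

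**4. The log route.** The expected number of uninfected placebo participants is 25 × 0.263 = 6.6. The chance of none is 0.737²⁵ = 0.0005. A plain log is then undefined in almost every trial. Dropping the zeros compares shedders with shedders: if the drug only prevents infection, the geometric mean ratio is about 1.0 even when the true reduction is 70%.

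**5. Which route the data would take.** Trials were simulated with 25 per arm, AUC 0 if uninfected and otherwise gamma with mean 27.5 and SD 15.2. Shapiro-Wilk, one of the checks in SAP 5.1.2, rejected normality at 5% in at least one arm in about 90% to 100% of trials, depending on how the drug acts. The check therefore tends to steer away from the untransformed t-test.

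**6. What a Fieller interval would give.** It contains every ratio ρ for which (m_T − ρ·m_C)² ≤ t² × (s_T² + ρ²·s_C²)/25. At means 6.09 and 20.3, the reduction of 70% has these limits:

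- 26% to 105% if both SDs are 17.8 (an upper limit above 100% would be shown as 100%);
- 49% to 82% if the CV is the same in both arms (palivizumab SD 0.3 × 17.8 = 5.34).

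At ρ = 1 the condition is exactly the unequal-variance t-test. With the same critical value, the ratio interval excludes no effect if and only if the difference interval does.

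**7. Choice of interval.** In the same simulation, with a true 70% reduction from pure prevention, a delta-method interval on the log ratio included no effect in about 21% to 22% of trials. For the difference interval it was about 13% to 14%, and Fieller matches that by construction. Fieller's coverage in this case was about 92% (20,000 trials). It was about 95% when the drug lowered viral load, with or without fewer infections.

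**The case against.** Several points on the other side are sound.

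- A reader might infer that the plan reports only a difference in means. It does not: the sentence after the quoted one provides a geometric mean ratio with an interval. That route is conditional and cannot take zeros, and it targets geometric rather than arithmetic means.
- A reader might infer that the trial has a 70% success criterion it cannot test. Protocol 9.2.2 gives 70% as a detectable effect, and Protocol 9.1 says that Part 2 is not meant to demonstrate significant differences.
- A reader might infer that the planned interval is faulty. The difference interval covers close to 95% in simulation. Poor coverage appears if it is divided by the observed placebo mean, which the plan never does.
- A reader might infer that the plan fixes a biosimilar margin on the wrong scale. No margin and no margin scale are set here.
- A ratio is stable across infection rates only if the drug removes a constant fraction of mean VL-AUC. Viral load is already in log10 copies, so a constant fold reduction in copies is a subtraction on this scale.
- Other outputs help. Arm means, SDs and CVs are tabulated, so a Fieller interval could be worked out afterwards. Infection incidence is compared by arm. VL-AUC is also tabulated in infected participants, although that subgroup is defined after dosing and is not a randomised comparison.
- The shift from 12.5 to 16.4 is small beside an interval of 4.1 to 24.3.

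These points limit the claim. They leave the gap in place: for the primary endpoint of an estimation study, no prespecified interval exists on the scale used for sizing.

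**Conclusion.** The point holds in a limited form. Part 2 is sized on a percentage reduction in arithmetic mean VL-AUC, and no planned route gives that reduction a confidence interval. The route that does give a valid interval, the untransformed t-test, is the one that the plan's own normality check would often set aside. What replaces it is either a log that is undefined at zero or a test with no estimate.

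For a constant 70% reduction, the reported difference would be 12.5 to 16.4 over the protocol's infection range, which is −12% to +15% around 14.2. This assumes zero AUC in uninfected participants and a proportional effect. The sample size is unaffected. The loss is in prespecification rather than in data, because the means and SDs needed will be collected anyway.

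**What to change.** In Protocol 9.6.2.2 and SAP 5.1.2 and 5.4.1, state that for VL-AUC, whatever the normality check shows, the report will give:

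- the difference in arithmetic means with an unequal-variance 95% interval;
- the ratio of arithmetic means (palivizumab/placebo), shown as a percentage reduction, with a Fieller 95% interval using the same critical value so that the two agree.

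Prespecify a bootstrap limit for when Fieller is unbounded or the palivizumab mean is 0. In the second case, resampling an all-zero arm only returns zero. The bootstrap should then draw the shedding proportion from its Clopper-Pearson limit, a method the SAP already uses. Under pure prevention this arises in (1 − 0.3 × 0.737)²⁵ = 0.2% of trials at a 70% reduction and (1 − 0.15 × 0.737)²⁵ = 5% at 85%.

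Rule out a plain log transform that drops zero AUCs, and keep Wilcoxon as a supporting p-value only. A margin for the biosimilar trial need not be stated here.

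The cost is one extra table row and the SAP wording, with no new data. The Fieller interval can be wide, or unbounded if the placebo mean is imprecise. At the design values that mean is 20.3/(17.8/√25) = 5.7 standard errors from zero, so an unbounded interval is unlikely. Coverage may fall a little below 95% when few palivizumab participants shed virus.

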#### 9.6.3. Participant accountability

The number of participants receiving Palivizumab or Placebo, receiving Challenge Virus, withdrawing from (also split by reason for withdrawal), and completing the study, and the numbers in each analysis set, will be summarised.

#### 9.6.4. Protocol deviations

Participant data will be reviewed for major protocol deviations prior to database lock and decisions will be documented within the meeting minutes. At this meeting, participants will be reviewed for their inclusion/exclusion from the analysis sets.

## 9.6.5. Demographic and baseline characteristics

Descriptive statistics of demographics (age, sex, height, weight, BMI, and ethnicity) will be presented by treatment group and across all participants. Medical history information will be listed. Other baseline characteristics will be defined in the SAP.

#### 9.6.6. Compliance to study treatment

Compliance with study drug will be computed for each patient as proportion of prescribed study drug actually taken.

# 9.6.7. Efficacy Endpoint(s)

Endpoints			Planned Inferential Analysis		
Area under the viral load-time curve (VL-AUC) of RSV-A Memphis 37b as determined by qRT-PCR on nasal samples collected twice daily starting two days post-viral challenge (Day +2) up to the end of quarantine.	t-test valid	if	assumptions		
Area under the viral load-time curve (VL-AUC) of RSV-A Memphis 37b as determined by cell culture on nasal samples collected twice daily starting two days post-viral challenge (Day +2) up to the end of quarantine.					
Area under the total symptom score-time curve (TSS-AUC) collected daily in the participant symptom diary card starting one day post-viral challenge (Day +1) up to the end of quarantine.					

Endpoints	Planned Inferential Analysis
Sum Total symptom score-time curve (TSS-Sum) collected daily in the participant symptom diary card starting one day post-viral challenge (Day +1) up to the end of quarantine.	MMRM for repeated measures, if underlying assumptions valid
Total weight of nasal discharge produced starting one day post viral challenge (Day +1) up to the end of quarantine.	t-test if assumptions valid
Total number of tissues used by participants starting one day post viral challenge (Day +1) up to the end of quarantine.	
Occurrence of at least two positive "quantifiable" qRT PCR measurements in nasal samples at different timepoints reported within two or more consecutive days starting two days post viral challenge (Day +2) up to the end of quarantine.	Chi-square test
Occurrence of at least two positive "detectable" qRT PCR measurements in nasal samples at different timepoints reported within two or more consecutive days starting two days post viral challenge (Day +2) up to the end of quarantine	
Number of days with quantifiable qRT PCR measurements in nasal samples starting two days post viral challenge (Day +2) up to the end of quarantine.	t-test if assumptions valid
Peak viral load of RSV-A Memphis 37b as defined by the maximum viral load determined by quantifiable qRT PCR measurements in nasal samples starting two days post viral challenge (Day +2) up to the end of quarantine.	t-test if assumptions valid
Incidence of symptomatic RSV infection, as defined by:  o Incidence of infection, and	Chi-square test (on both the composite and each component)
o At least one grade 2 symptom from one or more respiratory categories from the participant symptom diary card.	
Number of days with symptoms of grade 2 or more, starting one day post viral challenge (Day +1) up to the end of quarantine.	-test if assumptions valid
Peak symptom score defined by the maximum daily sum of Symptom score starting one day post viral challenge (Day +1) up to the end of quarantine.	-test if assumptions valid

